#### **8.4.3 Secondary Analysis (or Analysis of Secondary Endpoints)**

##### PSA decline of $\geq 50\%$ at 12 weeks post therapy initiation

The proportion of patients experiencing a PSA decline from baseline of at least 50% in PSA at 12 weeks following the initiation of study therapy will be presented with a 95% confidence interval.

##### Time to PSA progression (TTPP).

Time to PSA progression, is defined as the time interval between the date of treatment initiation and the date of either first documented PSA progression, or death due to any cause, whichever comes first. PSA is measured monthly until PSA progression as defined by the PSAWG2 criteria.

Duration of PSA response defined as the time between the first evaluation at which the response criteria are met and the first documentation of PSA progression or death. Early increase in PSA within 12 weeks, when followed by subsequent decline, is ignored in determining this endpoint.

Kaplan-Meier methods will be used to estimate the median time to PSA progression with a 95% confidence interval.

#### Relationship of abiraterone resistance status (primary vs acquired) and outcome

Radiographic progression free survival will be compared for patients with primary abiraterone resistance and acquired abiraterone resistance using a Cox proportional hazards model, and will be presented with a 95% confidence interval.

#### Time to confirmed development of $\geq 2$ new bone lesions

Time to development of  $\geq 2$  new bone lesions, defined as the time interval between the date of treatment initiation and the date of documented new lesions. Bone scans will be performed at week 8, 16, 24, and every 12 weeks thereafter; evaluation criteria is defined by the PSAWG2 criteria for bone scan evaluation. The time will be 'backdated' to when the  $\geq 2$  new lesions were detected if a second scan is done to confirm progression.

Kaplan-Meier methods will be used to estimate the median time to development of  $\geq 2$  new bone scans with a 95% confidence interval.

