Analyses of tissue biopsies, in combination with exploratory CTC analysis per our companion study protocol, therefore has the potential to generate a wealth of data about the expression profile of metastatic tumor. The relationship of XPO-1 expression to PSA

decline will also be evaluated along with the expression profile of metastatic tumor and clinical outcomes.

In the ongoing Phase 1 study in patients with advance solid tumors (NCT01607905), patients with mCRPC reported reduction in pain. The study will further determine which, if any, type of progression (e.g. pain, bone, etc.) is mitigated by selinexor therapy.

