### **2.4 Endpoints**

#### **2.4.1 Primary Endpoints**

Radiographic progression free survival (rPFS). This is defined from study start until one of the following events occurs:

- $\geq 2$  new bone lesions on Technetium bone scan. If  $\geq 2$  new lesions are detected at or 12 weeks following initiation of treatment, progression must be confirmed by the presence of  $\geq 2$  or more additional lesions to rule out bone scan flare as a cause of the radiographic changes.

- RECIST-defined tumor progression.
- Clinical deterioration requiring a change in prostate cancer therapy, or at clinician discretion
- Surgery or Radiation to treat a prostate cancer related indication
- Death from any cause.

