### 3.4 Duration of Therapy

In the absence of treatment delays due to adverse events, treatment may continue until:

- Disease progression
- Inter-current illness that prevents further administration of treatment
- Unacceptable adverse event(s), including any occurrence of grade 4 neurotoxicity
- Patients decides to withdraw from the study
- Significant patient non-compliance with protocol
- General or specific changes in the patients' condition render the patient unacceptable for further treatment in the judgment of the investigator.

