#### **8.4.2 Primary Analysis (or Analysis of Primary Endpoints)**

The primary end point is proportion of patients without evidence of radiographic progression at 16 weeks. This is defined from study start until one of the following events occurs:

- $\geq 2$  new bone lesions on Technetium bone scan
- RECIST defined tumor progression
- Cancer related pain requiring opiate analgesics
- Surgery or Radiation to treat a prostate cancer related indication
- Death from any cause

Radiographic PFS will be defined as the time from treatment initiation to the occurrence of either tumor progression in soft tissue according to modified RECIST criteria, identification of new lesions by bone scan ( $\geq 2$  new lesions confirmed  $\geq 12$  weeks later). If no such event exists, then rPFS will be defined as time from start of study until clinical deterioration requiring a change in prostate cancer therapy or at clinician discretion, surgery and/or radiation therapy to treat a prostate-cancer related indication, or death from any cause. PFS will be censored at the last scheduled disease assessment on study. PFS of living patients with no assessment on-study, and PFS of patients with no baseline assessment will be censored at enrollment.

rPFS will be estimated using the Kaplan-Meier product limit method. The median times to event with two-sided 95% confidence intervals will be estimated, together with the estimate of event rates at 6 and 12 months. The score statistic from the cox proportional hazards model will be used in the estimation of the hazard ratio and the associated 95% confidence interval will also be provided.

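### The Kaplan-Meier median for time to 2 or more new bone lesions censors deaths and exits for other progression; report a first-event cumulative incidence and state the censoring rule

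*Combined protocol and SAP*

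**What the plan says.** Section 8.4.3 has the endpoint "defined as the time interval between the date of treatment initiation and the date of documented new lesions". The planned analysis is a median with a 95% confidence interval: "Kaplan-Meier methods will be used to estimate the median time to development of" the lesions (the sentence ends with the word scans, evidently a slip). Neither a censoring rule nor a competing-risk method is given for this endpoint.

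The surrounding text determines what will happen:

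- Section 3.4 lists "Disease progression" among the reasons for ending treatment.
- Section 2.4.1 counts "RECIST-defined tumor progression", "Clinical deterioration requiring a change in prostate cancer therapy, or at clinician discretion", surgery or radiation for prostate cancer, and death as rPFS events separate from bone lesions.
- Bone scans are scheduled at screening and during treatment cycles (section 6.1.2.4, Table 6.1). Neither the end-of-treatment visit (6.1.3) nor the telephone follow-up (6.1.4) includes one.
- In the same section 8.4.3, time to PSA progression does count death, "or death due to any cause, whichever comes first". The bone endpoint does not.
- The only written censoring rule is in section 8.4.2 and is for another endpoint: "PFS will be censored at the last scheduled disease assessment on study".

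**The concern.** Kaplan-Meier knows only event or censored. A patient who dies, or who leaves for soft-tissue or clinical progression, without qualifying bone lesions is therefore censored, and the estimator assumes that his later risk equals that of patients still being scanned. Two problems follow.

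First, a reader will take the median as the time by which half of the patients have progressed in bone. With these exits censored it is not that time. The curve describes a setting in which nobody dies or progresses elsewhere.

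Second, even for that hypothetical setting, leaving must be unrelated to bone risk. Here patients leave because the same cancer is progressing. The confirmation rule adds to the problem. Under section 7.3, new lesions at the first reassessment need a second scan 6 or more weeks later, and a patient who leaves in between has no scheduled scan to confirm them.

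What is at stake is the description of activity in bone. Section 1.5 sets out that aim: "The study will further determine which, if any, type of progression (e.g. pain, bone, etc.) is mitigated by selinexor therapy". A figure for bone is useful there only if it can be set beside the other kinds of progression in the same patients.

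**Working it through.** **Plan's own figures.** The documents give no figure for this endpoint. The progression rates used below come from the two-stage design in section 8.2.1: stop if 10 or fewer of 18, reject the null if 36 or more of 54, 55% against 75% progression-free at 16 weeks. An exact binomial calculation gives type I error 0.0477 (stated 0.048), power 90.07% (stated 90.0%) and early stopping under the null 60.85% (stated 60.9%). The design reproduces.

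**Direction for first events.** Let h(u) be the bone hazard, S(u) the probability of being free of every event, and K(u) the Kaplan-Meier curve for bone alone. The cumulative incidence is the integral of S(u)h(u), and 1 minus Kaplan-Meier is the integral of K(u)h(u). Because K(u) is never below S(u), 1 minus Kaplan-Meier is never below the first-event incidence, whatever the bone share.

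**Size.** Inputs:

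- Total hazard H, assumed constant: −ln(0.55)/16 = 0.03736 per week under the null; −ln(0.75)/16 = 0.01798 under the alternative.
- Bone share s of first events: not in the documents. Assumed range 0.3 to 0.8.

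Formulas: 1−KM(t) = 1 − exp(−sHt); cumulative incidence CIF(t) = s(1 − exp(−Ht)); KM median = ln 2/(sH); CIF reaches 50% at −ln(1 − 0.5/s)/H, only if s exceeds 0.5.

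Worked case, null, s = 0.5, week 52: exp(−0.03736 × 52) = 0.143. So 1−KM = 1 − √0.143 = 62.1% and CIF = 0.5 × (1 − 0.143) = 42.8%.

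Each cell gives 1−KM / CIF in per cent; the last column gives KM median / time at which CIF reaches 50%, in weeks.

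| Progression-free at wk 16 | s | Week 16 | Week 24 | Week 52 | Median |
|---|---|---|---|---|---|
| 55% | 0.3 | 16.4 / 13.5 | 23.6 / 17.8 | 44.2 / 25.7 | 61.8 / never |
| 55% | 0.5 | 25.8 / 22.5 | 36.1 / 29.6 | 62.1 / 42.8 | 37.1 / never |
| 55% | 0.7 | 34.2 / 31.5 | 46.6 / 41.4 | 74.3 / 60.0 | 26.5 / 33.5 |
| 55% | 0.8 | 38.0 / 36.0 | 51.2 / 47.4 | 78.9 / 68.5 | 23.2 / 26.3 |
| 75% | 0.3 | 8.3 / 7.5 | 12.1 / 10.5 | 24.5 / 18.2 | 128.5 / never |
| 75% | 0.5 | 13.4 / 12.5 | 19.4 / 17.5 | 37.3 / 30.4 | 77.1 / never |
| 75% | 0.7 | 18.2 / 17.5 | 26.1 / 24.5 | 48.0 / 42.5 | 55.1 / 69.7 |
| 75% | 0.8 | 20.6 / 20.0 | 29.2 / 28.0 | 52.7 / 48.6 | 48.2 / 54.6 |

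Across shares 0.3 to 0.8 and both hazards, the excess is about 0.6 to 3.3 points at week 16, 1 to 6.5 at week 24 and 4 to 20 at week 52. At the KM median of 37.1 weeks (null, s = 0.5), exp(−Ht) = 0.25, so only 0.5 × 0.75 = 37.5% have had bone progression as their first event.

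**Scan schedule.** Trials of 54 patients were simulated on the planned scans (weeks 8, 16, 24, then every 12), assuming half of the non-bone events are found at scans. At week 24, null, s = 0.5, the means are 36.0% against 29.7%, in line with the table. At s = 0.7 under the null, both medians are recorded at week 36.

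**The case against.** The strongest counter-argument is that only death makes new bone lesions impossible. After soft-tissue or clinical progression a patient can still develop them; he is simply no longer scanned. Treating that exit as a competing event answers a different question from the stated one, which is time to bone lesions. If patients who progress elsewhere are also at higher risk in bone, Kaplan-Meier would understate that time-to-lesion risk. This stands. A reader might infer that the plan overstates bone progression without qualification, but the documents do not support that. The overstatement applies to bone progression as first on-study event; for the other target the direction is unknown.

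A reader might also infer that the plan will present Kaplan-Meier curves for each type of progression that fail to add up. It plans no such curves. Type of progression is an exploratory endpoint to be described, and no method is given. Nor are bone incidences at fixed times planned; event rates at 6 and 12 months are specified for rPFS only.

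The size can also be disputed. The gap is small at week 16 and smaller under the alternative. By week 52 under the null about 14% of patients are event-free, roughly 8 of 54 or 2 to 3 of 18, so sampling error is large. Eligibility requires a bone metastasis, which makes a high bone share plausible, and at 0.8 the medians differ by about 3 weeks. The scan schedule can hide the median gap altogether. All of this limits the consequence. It does not supply the missing censoring rule or make the exits uninformative.

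**Conclusion.** The point holds, with limits. As planned, the bone endpoint censors deaths and exits for progression of the same cancer. Read as bone progression occurring as first on-study event, the curve is too high and the median too early. Read as time to bone lesions regardless of other progression, the estimate depends on independent censoring that is doubtful here.

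The direction for first events is mathematical. The size rests on a constant hazard taken from the 16-week design rates and on an assumed bone share: a few points at week 16, and up to about 20 at week 52 under the null. With a share of 0.5 or less under the null, a finite Kaplan-Meier median can be reported although first-event incidence never exceeds 50%.

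This is a descriptive secondary endpoint. The 16-week primary test, the stopping rule and the sample size do not depend on it.

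**What to change.** In section 8.4.3:

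- Report the Aalen-Johansen cumulative incidence of confirmed bone progression as first event, with 95% confidence intervals at week 16 and at 6 and 12 months. Competing events are death and soft-tissue or clinical progression, including surgery or radiation for prostate cancer.
- State that patients who leave for toxicity or withdrawal without progression are censored at their last bone scan.
- Say how to classify a patient whose bone and soft-tissue progression appear at the same visit, and one who leaves with unconfirmed new lesions.
- Use the same cumulative incidences to describe type of progression; they sum to the total.
- Keep the Kaplan-Meier median as a secondary display, labelled as cause-specific and dependent on independent censoring.
- Correct scans to lesions in the sentence on the median.

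Adding death to the event, as for PSA progression, would deal with death only. The cost is a few lines of text and standard software, with no new data or patients. The downside is that a cumulative-incidence median may not be reached.

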#### Safety

Safety endpoints include incidence of worst grade adverse events; incidence of deaths and other serious and significant adverse events; and incidence of worst grade laboratory abnormalities. All recorded adverse events will be listed and tabulated by system organ class, preferred term, and by dose group and cohort and coded according to the Medical Dictionary for Regulatory Activities (MedDRA). Vital signs, physical examinations, clinical laboratory test, medical history, ECOG, and ECGs results will be listed and summarized by dose groups.

#### **8.4.4 Pharmacokinetic and pharmacodynamic analyses**

Serum selinexor concentrations, leukocyte collection, treated leukocyte lysate, and macrophage inhibitory cytokine-1 (MIC-1 mRNA) will be submitted to Karyopharm Therapeutics for analysis.

Summary statistics will be tabulated for the pharmacokinetic parameters of selinexor and study day. Geometric means and coefficients of variation will be presented for  $C_{\min}$ ,  $C_{\max}$ , AUC(TAU), and AUC(INF). Medians, minima, maxima will be presented for  $T_{\max}$ . Means and standard deviations will be provided for the remaining pharmacokinetic parameters. To describe the dependency on dose, scatter plots of  $C_{\min}$  and AUC(TAU) or AUC(INF) versus dose will be provided for each day measured. To assess the attainment of steady state, geometric mean  $C_{\min}$  values will be plotted by study day and dose.

Isolated leukocytes and serum samples will be studied for the temporal effects of KPT-330 on XPO1 inhibition and induction of macrophage-inhibitory cytokine 1 (MIC-1), a secreted biomarker reflecting the activation of p53 mediated apoptosis. Total RNA will be isolated from leukocytes of patients and the expression of XPO1 and MIC-1 will be measured by quantitative polymerase chain reaction analysis (qPCR). XPO1 mRNA induction will then

be assessed by comparing the fold increase of XPO-1 and MIC-1 expression from pre-dose levels as a function of selinexor dose and total time on treatment.

#### **8.4.5 Other Analyses/Assessments**

Additional correlative studies including pain scale changes measured by the brief pain inventory short form will be descriptively summarized.

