Secondary Objectives	
 
• To measure PSA changes at 12 weeks post-selinexor initiation
 
• To measure time to PSA progression
 
• To measure time to development of <math>\geq 2</math> new bone lesions
 
• To compare the relationship of abiraterone-resistance status (primary vs acquired) and treatment outcome
 
• To describe the safety profile of selinexor
 
• To measure reduction in pain for symptomatic patients based on the brief pain inventory short form.
 
• To determine the effect of selinexor on XPO-1 expression, leukocyte gene expression profile, and macrophage inhibitory cytokine-1 (MIC-1) mRNA expression
 
• To assess serum levels of selinexor as a function of dose and time since last dose
 

Study Design	Single agent phase II open label study of selinexor in patients with mCRPC with prior therapy with standard hormone ablation agents and abiraterone.
Number of patients	A maximum of 54 evaluable patients will be accrued for this study, provided the early stopping criteria are not met.
Duration of Therapy	In the absence of treatment delays due to adverse events, treatment may continue until: 
 
• Disease progression
 
• Inter-current illness that prevents further administration of treatment
 
• Unacceptable adverse event(s), including any occurrence of grade 4 neurotoxicity
 
• Patients decides to withdraw from the study
 
• Significant patient non-compliance with protocol
 
• General or specific changes in the patients' condition render the patient unacceptable for further treatment in the judgment of the investigator
 

Duration of Follow up	Patients will be followed for 30 days after completion of treatment or removal from study, or until death, whichever occurs first. Patients removed from study for unacceptable treatment related adverse event(s) will be followed until resolution or stabilization of all treatment related adverse events to Grade 2 or lower.
Duration of study	The study will reach the final procedure for primary outcome 24 months from the time the study opens to accrual. Data collection will be completed 36 months after the study opens to accrual.

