### **2.2 Secondary**

- To measure PSA changes at 12 weeks post-selinexor initiation
- To assess time to PSA progression
- To measure time to development of  $\geq 2$  new bone lesions
- To compare the relationship of abiraterone-resistance status (primary vs acquired) and treatment outcome
- To determine the effect of selinexor on persistent pain associated with bone metastasis using the brief pain inventory (BPI) short form.
- To describe the safety profile of selinexor in patients with metastatic castration-resistant prostate cancer.
- To determine the effect of selinexor on circulating leukocyte XPO-1 expression, leukocyte gene expression profile and macrophage inhibitory cytokine-1 (MIC-1) mRNA expression
- To assess serum selinexor trough levels as a function of dose and time since last dose

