#### **2.4.2 Secondary Endpoints**

- PSA decline of  $\geq 50\%$  at 12 weeks post therapy initiation
- Time to PSA progression. Defined as a rise in PSA of 50% above nadir value or 25% above baseline if there is no decline.
- Relationship of abiraterone resistance status (primary vs acquired) and outcome
- Time to confirmed development of  $\geq 2$  new bone lesions that cannot be attributable to bone scan flare
- Reduction in pain for symptomatic patients
- Safety
- Serum selinexor levels as a function of dose and time
- Pharmacodynamic analysis of selinexor impact on XPO-1 expression, leukocyte gene expression profile, and macrophage inhibitory cytokine-1 (MIC-1) mRNA expression

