### 6.1.3 End-of-Treatment Study Procedures

- To be completed within 30 days of the last dose of study drug.
- Physical examination
- Vital signs
- Performance Status
- Evaluation of adverse events
- Concomitant medications
- Brief Pain Inventory (BPI) short form
- Tumor biopsy -- optional, per companion Radiologically Guided Biopsy protocol of mCRPC, offered to patients treated at UCSF, UCLA, UC Davis, Oregon Health Sciences University, University of British Columbia
- Ophthalmologic exam including slit lamp examination and visual acuity prior to dilation, and a dilated fundoscopic evaluation and slit lamp examination.
- Laboratory evaluations
  - CBC with differential and platelet count
  - Blood chemistry assessment
  - PSA

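### The only analysis of the pain endpoint takes no account of added analgesia, palliative radiation or new therapy, so relief from those could be read as a selinexor effect

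*Combined protocol and SAP*

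**What the plan says.** The Abstract lists a secondary objective, "To measure reduction in pain for symptomatic patients based on the brief pain inventory short form". Section 2.2 words it as an effect of the drug: "To determine the effect of selinexor on persistent pain associated with bone metastasis using the brief pain inventory (BPI) short form". Section 2.4.2 lists the endpoint as "Reduction in pain for symptomatic patients", without defining symptomatic, the BPI item, the size of reduction or the time point.

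In the statistical section, pain is missing from the secondary endpoints in 8.1 and has no paragraph in 8.4.3. The whole analysis is one sentence in 8.4.5, which places pain among additional correlative studies and says that "pain scale changes measured by the brief pain inventory short form will be descriptively summarized".

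The BPI is taken at screening, on Cycle 1 Day 1, on Day 1 of each later cycle, and at end of treatment (6.1.1 to 6.1.3, Table 6.1). The end-of-treatment procedures carry the instruction "To be completed within 30 days of the last dose of study drug". Later follow-up is by telephone and lists no BPI (6.1.4). Baseline medications are recorded at screening, and concomitant medications at the other BPI visits.

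The first event list in 8.4.2 includes "Cancer related pain requiring opiate analgesics" and "Surgery or Radiation to treat a prostate cancer related indication". Section 2.4.1 and the second rPFS definition in 8.4.2 also include surgery or radiation but do not name opiates; they refer to clinical deterioration instead. Section 5.1 and Table 5.3 permit dexamethasone for nausea, anorexia or fatigue.

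**The concern.** A BPI score measures pain on whatever treatment the patient is then receiving. The protocol anticipates opiates and radiation during the study and permits steroids. A fall in BPI after any of these is not evidence about selinexor, and a single-arm trial has no comparison group in which the same relief would appear. Yet the objective in 2.2 asks for the effect of selinexor, and 1.5 gives pain relief reported in phase 1 as a reason for looking.

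Two things are at stake. First, the share of patients with reduced pain could be inflated by treatment given because pain was not controlled. Second, two endpoints could read one event in opposite directions: starting opiates is an event in the first 8.4.2 list, and the lower score that follows would appear as a pain reduction under 8.4.5. Because the handling is left open, it could also be chosen after the data are seen.

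**Working it through.** **1. The plan's own figures.** The plan gives no figure for pain. Its only design figures belong to the primary endpoint (8.2.1). Exact two-stage binomial, continuing with at least 11 of 18 and rejecting with at least 36 of 54:

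- Type I error = sum over x = 11 to 18 of P(X1 = x | 18, 0.55) × P(X2 ≥ 36 − x | 36, 0.55) = 0.0477 (stated 0.048).
- Power, same sum at 0.75 = 0.9007 (stated 90.0%).
- Early stopping, P(X1 ≤ 10 | 18, 0.55) = 0.6085 (stated 60.9%).

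All three reproduce. BPI enters none of them.

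**2. The passages side by side.** Take a patient with baseline bone pain who starts an opiate in Cycle 3.

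- First 8.4.2 list: an event.
- Section 2.4.1 and the second 8.4.2 definition: an event only if judged clinical deterioration.
- 8.4.5: the next BPI (next cycle, or end of treatment within 30 days of the last dose) enters the summary, since nothing excludes or separates it. If lower, it is a pain reduction.

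Radiation gives the same picture, and is an event under all the definitions. New anticancer therapy matters only if it starts before the end-of-treatment visit, because no later BPI is scheduled.

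**3. Illustration of size.** None of these inputs is in the documents. Assume no drug effect, baseline pain 5, response = 30% drop (5 × 0.30 = 1.5 points), normally distributed change with SD 1.5 or 2.0, and added analgesia lowering pain by 2 points.

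- No added analgesia: p0 = Φ(−1.5/SD) = Φ(−1.00) = 15.9% or Φ(−0.75) = 22.7%.
- Added analgesia: p1 = Φ((−1.5 + 2)/SD) = Φ(0.33) = 63.1% or Φ(0.25) = 59.9%.
- If a share a increases analgesia, the all-scores rate is (1 − a)p0 + a·p1. If those patients are not counted as responders, it is (1 − a)p0.

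| a | All scores (SD 1.5 / 2.0) | Increase not counted as response |
|---|---|---|
| 10% | 20.6% / 26.4% | 14.3% / 20.4% |
| 20% | 25.3% / 30.1% | 12.7% / 18.1% |
| 30% | 30.0% / 33.8% | 11.1% / 15.9% |

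So 16-23% becomes about 21-34% when all scores are used.

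**4. Sensitivity to a prior rise in pain.** Analgesia is usually added because pain has risen. If it first rose 1 point, the net shift is −1 and p1 = Φ(−0.33) = 36.9% or Φ(−0.25) = 40.1%. At a = 20-30% the all-scores rate is then about 20-28%. If it first rose 2 points, the net shift is 0, p1 = p0, and there is no inflation.

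**5. A second illustration, in patients.** Assume 30-70% of 54 are symptomatic (16 to 38), 10-40% of them start opiates, 30-70% of starters then report lower pain, and 20% of the others do.

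- All scores: from 0.1 × 0.3 + 0.9 × 0.2 = 21% to 0.4 × 0.7 + 0.6 × 0.2 = 40%.
- Opiate start not counted as improvement: from 0.6 × 0.2 = 12% to 0.9 × 0.2 = 18%.
- Gap: 0.1 × 0.3 = 3 points to 0.4 × 0.7 = 28 points, or 16 × 0.03 = 0.5 to 38 × 0.28 = 10.6 patients who would be progressed under the first 8.4.2 list and improved on pain.

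**The case against.** The strongest reply is that 8.4.5 is silent rather than wrong. A reader might infer that the plan prescribes unadjusted scores, averaged visit by visit, whatever else was given. It does not say so; it states no rule. That stands, but following the sentence as written still leaves the relief from other treatment inside the summary.

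The conflict between the endpoints is also narrow. It follows directly only from the first 8.4.2 list. If an opiate start is handled as progression, treatment ends under 3.4 and the end-of-treatment BPI is normally the only one left. rPFS and pain are different endpoints, and some discordance between them is not an error in itself. All this limits the number of affected scores without removing them.

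A reader might infer that patients who leave with worse pain vanish from the data. The scheduled end-of-treatment BPI partly answers this. What remains is that scores in later cycles come only from patients still on treatment, and no missing-data rule is given.

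A reader might also infer that a false positive on pain would drive a decision. The documents do not support that: the decision rule in 8.2.1 uses progression-free status at 16 weeks only, and 1.5 describes exploration.

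Finally, the illustration depends on its inputs. At 10% the shift is modest, and a prior rise in pain shrinks it or removes it. Counting every early stop as a non-responder would pull the rate down, including for toxicity stops unrelated to pain. Both points stand and shape the fix.

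**Conclusion.** The concern holds as a gap in the analysis of a secondary endpoint. The plan attributes pain reduction to selinexor but summarises BPI changes with no account of analgesic increases, palliative radiation or new therapy, and without a control arm the summary cannot support that attribution. Opiates and radiation are the main exposure; new therapy is confined to the window before the end-of-treatment visit. The progressed-yet-improved case arises under the first 8.4.2 list, which must be reconciled with 2.4.1 and the second rPFS definition in 8.4.2.

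The size is illustrative. With 10-30% of symptomatic patients increasing analgesia, the response rate with no drug effect moves from 16-23% to about 21-34% if pain had not risen beforehand, and by less or not at all if it had. This rests on an assumed responder threshold, baseline, SD and analgesic effect. Type I error, power, sample size and stopping rules for the primary endpoint are unchanged. The plan should be amended, but the primary result does not depend on it.

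**What to change.** In 8.4.5, for patients symptomatic at baseline:

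- Pre-specify the BPI item, the threshold for symptomatic, which BPI is the baseline (screening or Cycle 1 Day 1), the size of reduction and the time point.
- Report the proportion with a pain reduction and no new or increased analgesic, palliative radiation or new anticancer therapy since baseline, using the concomitant medication and treatment records already collected.
- Report the all-scores summary beside it, with the number still on treatment at each visit.
- Flag steroid use.
- Report early stops by reason, with non-responder counting as a sensitivity analysis.
- Separate end-of-treatment BPIs taken after a new therapy.

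List the endpoint in 8.1 so that it matches 2.4.2, and reconcile the event definitions in 2.4.1 and 8.4.2.

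The cost is SAP wording and some coding of medication records, with no new visit or change in sample size. The documents do not say whether analgesic doses are recorded, so the case report form should be checked for dose and dates. The downside is a lower reported pain-response rate.
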